## **Research question and objectives**

### **Research question**

Is the incidence and prevalence of Fabry associated clinical events (FACEs) (cardiac, renal, and cerebrovascular) associated with sex, genotype, phenotype at time of diagnosis, biomarkers, and Fabry specific therapy?

## **Objectives**

To investigate time to first Fabry associated clinical events (FACE) (cardiac, renal, and cerebrovascular) with particular focus on Migalastat clinical outcomes and treatment outcomes preceding Migalastat therapy.

To investigate the incidence and prevalence of FACEs with respect to Fabry specific treatment, Migalastat, ERT or no treatment.

To describe FACEs in accordance with different geno- and phenotypic groups.

To investigate the incidence and time to a first fatal or non-fatal cardiac, renal and cerebrovascular clinical event, separated by each category.

### **Primary objective**

To investigate time to first Fabry associated clinical events (FACEs) (cardiac, renal, and cerebrovascular) with particular focus on Migalastat clinical outcomes and treatment outcomes preceding Migalastat therapy.

### **Secondary objectives**

To investigate the incidence and prevalence of FACEs with respect to Fabry specific treatment, Migalastat, ERT or no treatment.

To describe FACEs in accordance with different geno- and phenotypic groups.

To investigate the incidence and time to a first fatal or non-fatal cardiac, renal and cerebrovascular clinical event, separated by each category.

### **Exploratory objectives**

To describe disease progression with focus on organ involvement.

## **Research methods**

### **Study design**

Observational, retrospective, single-center study originating from the Danish National Fabry Centre, Centre of Cancer and Organ Disease, Department of Medical Endocrinology, Copenhagen University Hospital, Rigshospitalet. Patients are enrolled at the time of sampling leading to a genetically verified diagnosis of Fabry disease. Patients are followed from the day of enrolment until 31st of December 2022, having received yearly or bi-yearly evaluation during follow-up.

### **Method**

Retrospective study of prospectively collected patient data with use of secondary patient data from both paper and electronic patient files. All patients are treatment naïve at time of diagnosis, which is defined as time point for a verified Fabry associated genetic mutation in the GLA gene. A baseline time point is further defined by switch of Fabry specific treatment. Both Migalastat and ERT will be studied retrospectively. Also untreated patients will be studied by assessment of relevant clinical and laboratory variables. The patients have been followed from 01.01.2001 until

31.12.2022. All patients with Fabry disease both receiving specific Fabry medication and untreated patients have been offered assessment yearly or every other year by thorough workup, including targeted examinations of organ function and symptoms known to be associated with Fabry Disease.

## **Endpoints**

### **Primary endpoints**

The primary endpoint is time to first FACE (cardiac, renal, or cerebrovascular events) since each baseline, with particular focus on the added value of the recent addition of Migalastat as a treatment option.

FACEs are defined as the following:

- Cardiac clinical events:
  - Myocardial infarction
  - New symptomatic arrhythmia requiring medication, direct current cardioversion, or interventional procedure (e.g., ablation, pacemaker, or defibrillator implantation)
  - Unstable angina defined by national practice guidelines and accompanied by electrocardiographic changes and non-ST segment elevation myocardial infarction [UA/NSTEMI]) and accompanied by electrocardiographic changes
  - Congestive heart failure requiring hospitalization
  - Any major cardiac medical procedure (e.g., valve replacement, stent-implantation, transplant or persistent atrial fibrillation)
- Cerebrovascular clinical events
  - Stroke (documented by a physician)
  - Transient ischemic attack (documented by a physician)
- Renal clinical events
  - Doubling of serum creatinine level from the start of analysis (2 consecutive values)
  - End-stage renal disease (ESRD) requiring long-term dialysis or transplantation
- Death due to FACEs

All FACEs will be analyzed together as a composite endpoint and separately in each category (cardiac, cerebrovascular, and renal).

## **Secondary endpoints**

### **The secondary endpoints**

- The prevalence of FACEs from each baseline (diagnosis, and start of treatment) to compare between Migalastat-treated, ERT-treated patients and non-treated patients
- The incidence of FACEs from each baseline (diagnosis, and start of treatment) to compare between Migalastat-treated, ERT-treated patients and non-treated patients

- Time to the first cardiac, cerebrovascular, and renal clinical event separately by each specific category (including death in these categories) from start of treatment or baseline
- Incidence of cardiac, cerebrovascular, and renal clinical events separately by each specific category (including death in these categories)
- Occurrence of cardiac, cerebrovascular, and renal clinical events separately by each specific category (including death in these categories)
- Annualized rate of change in eGFR based on the Chronic Kidney Disease Epidemiology Collaboration equation (eGFRCKD-EPI) over time to compare between Migalastat-treated, ERT, and untreated patients
- The prevalence and incidence of a clinically significant change in mGFR and/or eGFR (according to KDIGO guidelines rapid progression is defined as a sustained decline in eGFR of more than 5 ml/min/1.73 m^2 /yr) from each baseline (diagnosis, and start of treatment) to compare between Migalastat-treated, ERT-treated patients and non-treated pts
- The prevalence and incidence of micro (> 30 mg/g creatinine) or macroalbuminuria (> 300) by urinary albumin/creatinine ratio (ACR) or urinary 24 h protein excretion from each baseline (diagnosis, and start of treatment) to compare between Migalastat-treated, ERT-treated patients and non-treated pts

## **Exploratory organ specific Endpoints**

Reflecting the programme of the annual clinical examinations and questionnaires of the Danish Fabry patients.

**Lung capacity:** clinically significant changes in spirometry measures of obstructive and restrictive lung function evaluate by body plethysmography

- Forced expiratory volume after 1 second (FEV1)  
A clinically relevant change is defined as 25% decrease from baseline or as incident volume of 20% below predicted value according to an age- and sex-adjusted reference range.
- Forced vital capacity (FVC)  
A clinically relevant change is defined as 25% decrease from baseline or as incident volume of 20% below predicted value according to an age- and sex-adjusted reference range.

## **Neurological, audiological assessments**

- Standardized sweat test (hypo, normo, hyperhidrosis), standard unit of measure: mg pr. 30 minutes

### **Standardized tilt-test (Presence of orthostatism – yes/no)**

- Heart rate variability (Age-dependent – impaired vs not)
- Audiogram (Impaired vs. not)
- Autonomic nerve function (small fibre assessment))
- Presence of Fabry associated abnormalities by brain MRI

### **Ophthalmological and dermatological assessments**

- Presence of cornea versiculata
- Presence of angiokeratoma

### **Composite phenotypic score**

- Mainz Severity Score Index (Composite score)

### **Cardiac function** (evaluated by echocardiography)

- Left ventricular mass index (LVMi)
- Left ventricular ejection fraction (LVEF)
- Fractional shortening
- Left ventricular end diastolic and systolic volumes
- Mid-wall fractional shortening (MWFS)
- Left ventricular wall thickness
- NT-proBNP and high sensitive Troponin T – will be analysed from the Danish Fabry biobank.

### **Renal function**

Laboratory parameters:

- serum creatinine
- urine creatinine
- urine protein
- urine albumin
- urine ACR
- measured glomerular filtration rate by 99Tc-DTPA or 51Cr-EDTA

### **Patient reported outcomes (PRO)**

- SF-36 Health Questionnaire (Composite score)

- NHP-Health Profile (Daily living questionnaire – composite score)
- Major Depression Inventory (Becks Depression Index II - Composite score)

### **Pharmacodynamic Endpoints**

Pharmacodynamic endpoints will be assessed by evaluations comparing Migalastat-treated and untreated patients and/or Migalastat-treated and ERT-treated patients:

- Plasma lyso-Gb3
- WBC  $\alpha$ -Gal A enzyme activity
- Urinary and plasma Gb3, lyso-Gb3,  $\alpha$ -GAL A enzyme activity
- Neutralizing antibodies with ERT

### **Evaluation tools**

Data extraction from electronic and paper medical records. No specific evaluation test or tool required.

### ***Setting***

### **Study population**

All patients from the Danish National Fabry Centre will be included, estimating the inclusion of 115 individuals (sex ratio [female:male] – 2:1). Pre-specified subgroups includes: non-amenable/ amenable to Migalastat, males/females.

### **Inclusion criteria**

- Established diagnosis of Fabry Disease based on genetic testing and alpha Gal-A activity in males and females.
- Data from baseline visit and at least one follow-up visit.

### **Exclusion criteria**

Absence of data from baseline visit.

### **Treatments**

### **Study treatment**

No treatment will be evaluated prospectively. However, patients will be grouped according to treatment received during the treatment period (Migalastat, enzyme-replacement therapy or no treatment).

Patients who are switched from one treatment to another will be grouped according to current treatment at the assessment time point (if possible, according to a new baseline before switching).

Details of this procedure will depend on available information and numbers and cannot be described until all patients data have been collected.

## Symptomatic therapies

Data on nonspecific Fabry therapy such as ace enzyme inhibitors (ACE-I), angiotension-II blockers (AT-II), anticoagulants, statin, antiarrhythmic therapy, asthma/bronchodilator therapy, antidepressive therapy, as well as use of analgesics and other important concomitant medication will be recorded.

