#### Variables concerning concomitant medication

The included concomitant medication to be recorded is restricted to medications believed to be of clinical interest. Medication will be recorded as to their use at inclusion and regarding their change throughout the study if possible.

Concomitant medication at inclusion	
ACE-I/ ARB	Yes No
Beta-blocker	Yes No
Ca-blockers	Yes No

Diuretics	Yes No
Statins	Yes No

Date (Date)	Drug (Name)	Action* (Categorical)	Dose (Integer)	Dose interval (Comment)	Comment (Comment)
----------------	----------------	--------------------------	-------------------	----------------------------	----------------------

\*Action is restricted to four levels: Initiation, decrease, increase, cessation.

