10. CONCOMITANT MEDICATIONS

Concomitant medications will be defined as medications taken on or after the date of enrollment into the study and through the duration of the study.

If the medication stop date is before the enrollment date, such a medication is considered a previous medication and will not be analyzed, with exception of the previous ERT therapy and the previous migalastat treatment but will be listed.

For prior ERT or migalastat therapy, an overall prior exposure table will be presented by treatment group at baseline. If the stop date is missing or therapy is continuing, the date to calculate prior exposure will be the study enrollment date. A data listing will include dose and infusion frequency.

Concomitant medications will be coded according to the WHO-DRUG and will be summarized by treatment group using the Effectiveness and Safety Populations.

All reports in this section will provide the number of patients who received a concomitant medication by preferred drug name, Anatomical Therapeutic Chemical (ATC) class, and overall. A patient who received multiple agents within an ATC class will only be counted once for that class. Similarly, a patient who received a drug multiple times will only be counted once for the preferred drug name. Patients will be accounted into the group at the time of concomitant medication start date.

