13.6. Secondary Endpoint: Prevalence of FACEs by Category

Prevalence of cardiac, cerebrovascular, and renal clinical events separately by each specific category (including death in these categories) will be analysed as in Section 13.3 for the composite FACEs.

13.7. Secondary Endpoint: Estimated Glomerular Filtration Rate to Compare Migalastat-treated, ERT Treated, and Untreated Patients

Estimated GFR will be summarized using descriptive statistics by treatment at diagnosis date. Descriptive statistics will be displayed for change from Analysis Start Date (time of diagnosis or treatment start) to e.g. time points such as the date of the first treatment switch, date of the treatment to migalastat or any other time points of interest.

For dialysis and transplant patients, the Analysis Start Date for eGFR will be reset to the last value before dialysis start or before transplantation and used thereafter.

Analysis Methods

Data will be listed. Listings will contain flags indicating therapy change. Spaghetti plots will indicate what treatment group a patient was on at the time of measurement.

Longitudinal analysis using Mixed Model for Repeated Measures (MMRM) will be used to analyze data over time. Trends over time using adjusted means will be plotted. Missing post-Analysis Start Date measurements will not be imputed as MMRM method allows for missing values. This analysis only accounts for changes over time regardless of therapy.

Covariates are:

- sex
- enrollment age as a continuous variable
- enrollment eGFR as a continuous variable
- proteinuria based on the UPCR value at enrollment
- LVMi at enrollment
- history of cardiac, cerebrovascular, and renal clinical events (a binary endpoint based on the composite event) prior to enrollment
- length of treatment for Fabry disease

If the measurements are not available, measurements prior to and closest to the Analysis Start Date will be used. In case that more than 50% of values are missing for a given covariate, it will be dropped from the analysis.

Additionally, the annualized rate of eGFR change will be calculated as the slope of the individual patients' regression equations over time. The annualized rate of change will be analyzed using t-test for migalastat-treated versus untreated patients. This analysis only accounts for changes over time regardless of therapy.

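### ACE-inhibitor/ARB use is recorded but enters no renal comparison of migalastat, ERT and untreated patients, so any unequal use would be attributed to the Fabry therapy

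*Protocol*

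**What the plan says.** **What is collected.** The Protocol section on symptomatic therapies begins its list of drugs to record with "Data on nonspecific Fabry therapy such as ace enzyme inhibitors (ACE-I), angiotension-II blockers (AT-II". The section on concomitant medication restricts the list to drugs thought clinically relevant and puts ACE-I/ARB first, as a Yes/No field at inclusion, with a dated log of changes. It adds: "Medication will be recorded as to their use at inclusion and regarding their change throughout the study if possible".

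**What the comparison is for.** The Protocol's secondary endpoints include the annualised eGFR change "over time to compare between Migalastat-treated, ERT, and untreated patients". Rapid GFR decline and micro- or macroalbuminuria are compared across the same three groups.

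**What the SAP does with the drug data.** Section 10 is descriptive: "Concomitant medications will be coded according to the WHO-DRUG and will be summarized by treatment group using the Effectiveness and Safety Populations". A patient is counted in the group that applied on the date the drug was started.

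**What the renal analyses contain.** The covariates of the eGFR mixed model (SAP 13.7) are sex, age, eGFR, "proteinuria based on the UPCR value at enrollment", LVMi, history of clinical events and "length of treatment for Fabry disease". For the slopes: "The annualized rate of change will be analyzed using t-test for migalastat-treated versus untreated patients". Of the mixed model, and again of the slope analysis, the SAP says: "This analysis only accounts for changes over time regardless of therapy". An alternative analysis splits the eGFR data by Fabry treatment period. Sections 13.8 and 13.9 borrow the prevalence and incidence methods of 13.2 and 13.3.

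**The concern.** The groups are not randomised. Follow-up starts in 2001, and the Protocol says migalastat became available in 2016, so migalastat periods fall late while untreated periods can fall much earlier. Background renal treatment may therefore differ between them. If ACE-I/ARBs alter albumin excretion or eGFR decline, which I take here as an assumption, a difference in their use would produce a difference in these endpoints with no effect of the Fabry drug.

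Three secondary endpoints are exposed: eGFR slope, rapid GFR decline and albuminuria. SAP 3.2 sets two-sided 0.05 for these comparisons without multiplicity adjustment, so a nominally significant renal difference could be reported without any check on co-medication.

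**Working it through.** **Step 1. Does any renal analysis use ACE-I/ARB?** The documents give no power or sample-size figure to reproduce; the SAP says the size was not determined statistically. The check is a reading of each analysis.

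| Analysis | Contrasts treatments? | ACE-I/ARB used? |
|---|---|---|
| eGFR mixed model, 13.7 | No treatment term listed | No |
| eGFR slope t-test, 13.7 | Migalastat vs untreated | No covariates at all |
| eGFR by treatment period, 13.7 | Yes | No |
| Rapid GFR decline, 13.8 | Yes, crude ratio and rate | No |
| Albuminuria, 13.9 | Yes, crude ratio and rate | No |
| Subgroups, SAP 12 | Some | No |
| Protocol strata (Descriptive statistics) | Yes | No |

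The laboratory analyses in SAP 15.6 follow 13.7 and inherit the gap.

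**Step 2. Size for the eGFR slope.** The documents give neither use by group nor an effect size, so both inputs are assumptions.

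- d = use in migalastat minus use in untreated: -0.5 to +0.5.
- g = slowing of eGFR loss with ACE-I/ARB: 0.5 to 1.0 ml/min/1.73 m² per year.
- Spurious slope difference = d × g.

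| d | g = 0.5 | g = 1.0 |
|---|---|---|
| -0.5 | -0.25 | -0.5 |
| -0.2 | -0.1 | -0.2 |
| 0 | 0 | 0 |
| +0.2 | +0.1 | +0.2 |
| +0.5 | +0.25 | +0.5 |

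**Step 3. Effect on the t-test.** Assume 30 migalastat and 40 untreated patients, a between-patient slope SD of 2 to 4, and a spurious difference of 0.4 (d = 0.4, g = 1.0). By normal approximation:

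- SE = SD × √(1/30 + 1/40) = SD × 0.2415, that is 0.483 (SD 2) or 0.966 (SD 4).
- Shift = 0.4/SE = 0.828 or 0.414.
- False-positive rate = 1 - Φ(1.96 - shift) + Φ(-1.96 - shift) = 0.131 or 0.070, against a nominal 0.05.

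A spurious difference of -0.4 gives the same rates.

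**Step 4. Size for albuminuria prevalence.** Section 13.9 counts patients above thresholds, so the relevant quantity is a prevalence ratio. Assume 40% prevalence without ACE-I/ARB and a risk ratio R of 0.5 to 0.8 with it. Group prevalence = 0.4 × (1 - p + p × R), where p is the share of users.

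- Use 60% vs 20%, R = 0.5: 0.28/0.36 = 0.78.
- Use 60% vs 20%, R = 0.8: 0.352/0.384 = 0.92.
- Use reversed (20% vs 60%): 0.36/0.28 = 1.29 and 0.384/0.352 = 1.09.
- Equal use: 1.00.

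Steps 2 to 4 cover only a direct drug effect. Confounding by indication is not included.

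**The case against.** **The consequence is conditional.** A reader might infer that the renal effect of these drugs is in fact being credited to the Fabry therapy, probably in its favour, with co-use highest on migalastat. The documents do not support that. They contain no data on ACE-I/ARB use by group or period, and the bias is zero if use is equal. Patients with albuminuria or falling eGFR may be the ones who receive these drugs, so a group with more use could look worse. This objection stands in full.

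**The Section 10 table would show an imbalance.** Only in part. It assigns a drug to the group at its start date. An ACE-I/ARB begun while untreated and continued through years of migalastat counts under untreated. The table shows where a drug began, not who took it in the period analysed, and it adjusts nothing.

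**Proxies are already in the plan.** Proteinuria and eGFR at enrolment are covariates in the mixed model, renal impairment and proteinuria are subgroups, and the Protocol stratifies by baseline organ involvement and allows further analyses. These are partial proxies for indication. The covariates are absent from the t-test and the crude rates, and none of the proxies reflects a drug started later.

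**The t-test and crude rates adjust for nothing, so ACE-I/ARB is only one omission.** This is fair. It is a reason to replace the t-test with an adjusted model, not a reason to leave a collected renal co-medication out of that model.

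**Conclusion.** The omission is established from the text: ACE-I/ARB use is collected and enters no renal comparison between treatment groups. What follows is conditional. If use differs between groups or periods, part of any renal difference would be misattributed to the Fabry therapy.

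Under the assumptions in the working, the spurious slope difference lies between -0.5 and +0.5 ml/min/1.73 m² per year, with zero included. At 0.4 in either direction, the false-positive rate of the t-test rises from 0.05 to between 0.07 and 0.13, a modest inflation. The distortion of an albuminuria prevalence ratio at a 40-point difference in use is 0.78 to 0.92, or 1.09 to 1.29 if the imbalance is reversed. None of these inputs comes from the documents.

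The exposed analyses are the slope t-test, the treatment-period analysis and the crude rates in 13.8 and 13.9. The mixed model is not exposed in the same way, because it contrasts no treatments. The point concerns secondary endpoints and is worth acting on because the change is cheap.

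**What to change.** 1. **SAP 13.7, slopes.** Replace the unadjusted t-test with a regression or mixed slope model containing a treatment term, the covariates already listed, and ACE-I/ARB use (yes/no) at the Analysis Start Date. For migalastat versus untreated that date is diagnosis, which the SAP equates with enrolment, so the inclusion field should supply the value. Measure length of Fabry treatment up to the Analysis Start Date, so that it does not overlap with the treatment term.
2. **SAP 13.7, treatment periods.** Use ACE-I/ARB status at the start of each period.
3. **SAP 13.8 and 13.9.** Present the results also by ACE-I/ARB use at period start.
4. **SAP 10.** Tabulate ACE-I/ARB use during each treatment period, with the completeness of the record.

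Two apparent remedies should not be relied on. Adding the term to the existing mixed model corrects no treatment contrast, because that model has no treatment term. Censoring follow-up when ACE-I/ARB is started or stopped may be informative, since a start can be prompted by the outcome being measured. It should be left out or labelled exploratory.

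**Cost.** SAP wording, one binary covariate already on the form, and a few tables. Status may be missing at some later treatment starts, because changes are recorded only where possible. Adjustment at baseline or period start does not remove the effect of drugs begun later, and it may not remove confounding by indication. The report should say so.

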## Other measures

If possible, information on comorbidities at each treatment start and switch will be recorded.

## Study workflow

Fabry patients entered the study at their baseline visit (first visit in the center) from 2001 with last follow-up December 2022. Patient data will be grouped for the whole duration of the defined study period, with individual datapoints registered at the specific date of event/measurement. Ideally the datapoints will be used according to their specific dates but may be aggregated according to availability. Details is further described in the statistical analysis plan.

